For all female subjects, urine pregnancy tests will be performed at all visits, and a positive pregnancy test will result in immediate discontinuation. At baseline, 12 weeks, and 24 weeks, subjects will be counseled regarding lifestyle modification (see Methods). Subjects will continue to receive care from their regular medical providers, including hepatologists, throughout the study. Any subject not under the care of a hepatologist who is found at screen to have $\geq 5\%$ liver fat and significantly elevated AST or ALT will be offered referral to the hepatology clinic.

Screen: (1) Informed consent; (2) Detailed H&P, including medications and alcohol habits; (3) blood sampling for IGF-1, CBC, HbA1c, fasting glucose, AST, ALT, total bilirubin, Hepatitis B sAg, Hepatitis C antibody; (4) ^1H -MRS/MRI of abdomen in fasting state for quantification of liver fat. (This scan will also be used to assess VAT and SAT for those eligible subjects participating in the baseline visit.)

Randomization and Study Drug: After the screening visit, eligible patients who wish to participate will be randomized in a 1:1 ratio to Norditropin vs. no treatment. The study will not be blinded and placebo will not be used to avoid daily injections without benefit for subjects randomized to no treatment. Randomization will be stratified by gender and Vitamin E use. The starting dose of Norditropin will be 0.5 mg daily, which is a recommended dose for restarting growth hormone in young adults with GHD during the transition from adolescence to adulthood (70). IGF-1 will be checked at 2, 4, 6, 12, and 18 weeks, and will be reviewed by the PI. Active dose adjustments will be performed per algorithm as follows. A 20% dose increase will be performed for any Norditropin subject with IGF-1 SDS ≤ 0 . Conversely, a 20% decrease in dose will be performed for any Norditropin subject with IGF-1 SDS > 2 .

| Norditropin Dosing Algorithm (starting dose 0.5 mg) | | |
|--|-------------------------------|---------------------|
| IGF-1 SDS ≤ 0 | $0 < \text{IGF-1 SDS} \leq 2$ | IGF-1 SDS > 2 |
| 20% dose increase | maintain dose | 20% dose reduction* |
| *Subjects with persistent IGF-1 SDS > 2 after 2 dose reductions will be discontinued from the study. | | |

Baseline Visit:

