Lifestyle Counseling: Subjects will receive lifestyle counseling from study MDs or nutritionists at the baseline, 12 week, and 24 week visits, with recommendations and resources provided based on the 2010 Dietary Guidelines for Americans (http://www.cnpp.usda.gov/sites/default/files/dietary_guidelines_for_americans/PolicyDoc.pdf) and the 2008 Physical Activity Guidelines for Americans (<http://health.gov/paguidelines/guidelines/summary.aspx>). Emphasis will be placed on physical activity (150+ minutes weekly); reduction of saturated fats, total fats, and sugary beverages; and increased consumption of fruits and whole grains.

VII. Biostatistical Analysis

Statistical Consideration – Data Interpretation: The primary endpoint will be change in hepatic fat as measured by ¹H-MRS after 24 weeks of randomized treatment. Secondary endpoints will include changes in ALT, AST, GGT, VAT, CRP, adiponectin, IGF-1, lipids, fasting and 2-hour glucose and insulin, HbA1c, and respiratory quotient measured by indirect calorimetry. Permuted block randomization will be performed, stratified by gender and use of Vitamin E.

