Analysis will be intention-to-treat, using all available data from all subjects. Wilk-Shapiro test will be used to assess for normality of distribution of all variables, and variables that are not normally distributed will be appropriately transformed. Baseline variables will be compared between treatment groups, and any baseline variable that is statistically different between treatment groups will be adjusted for in subsequent analysis. Changes in variables measured only at baseline and 6 months, including the primary endpoint of liver fat, will be initially assessed using a two-sample t-test comparing mean changes between treatment groups. A critical alpha level of 0.05 will be used as the threshold for significance, and all statistical tests will be two-tailed. Subsequently, adjusted analyses will be performed including as covariates any baseline characteristics that differ between treatment groups and any differential changes in nutritional intake or physical activity between treatment groups over the study duration. For variables measured at ≥ 3 timepoints throughout the study (e.g., IGF-1, AST and ALT), we will analyze the longitudinal data using general linear mixed effects modeling, testing for time x treatment group interaction. The primary analysis will be an intention to treat analysis using all available data. We will consider secondary multiple imputation based analyses if necessary.

A supplementary analysis will be performed assessing stimulated growth hormone levels in response to Arginine testing. Using peak GH as the independent variable, we will assess the hypothesis that peak GH will be negatively associated with liver fat quantity.

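### Gender and Vitamin E stratify the randomisation but enter no analysis, so the primary liver-fat t-test is conservative if either factor predicts change in liver fat

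*Combined protocol and SAP*

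**What the plan says.** The design is stated twice. Section V (Randomization and Study Drug) says eligible patients "will be randomized in a 1:1 ratio to Norditropin vs. no treatment" and "Randomization will be stratified by gender and Vitamin E use". Section VII (Data Interpretation) adds the method: "Permuted block randomization will be performed, stratified by gender and use of Vitamin E". No block size is given.

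Section VII then sets out the analysis:

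- Primary endpoint, grouped with the other variables measured only at baseline and six months: "including the primary endpoint of liver fat, will be initially assessed using a two-sample t-test comparing mean changes between treatment groups".
- Covariates: "any baseline variable that is statistically different between treatment groups will be adjusted for in subsequent analysis". The later adjusted step repeats this ("adjusted analyses will be performed including as covariates any baseline characteristics that differ between treatment groups") and adds differential changes in diet or activity.
- Variables with three or more timepoints: "general linear mixed effects modeling, testing for time x treatment group interaction".
- Error rate: "A critical alpha level of 0.05 will be used as the threshold for significance, and all statistical tests will be two-tailed".

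Neither gender nor Vitamin E is named as a term in any of these.

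**The concern.** Stratified blocks hold the arms nearly equal on gender and Vitamin E. If one of these factors predicts the change in liver fat, its contribution is largely removed from the difference between arm means. An unadjusted t-test still counts that variation in its error term. The standard error is then too large for the design that was run: the test rejects too rarely under the null and the 95% interval covers too often.

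The plan's own adjustment step cannot be relied on to correct this. It waits for a baseline difference between arms, which stratification is there to prevent. With about 19 evaluable patients and power of only 80%, precision is worth keeping where it can be had.

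**Working it through.** **Inputs from Section VII (Sample Size and Power Calculations).** SD 3.1 points, difference 4.2 points, 24 randomised, up to 20% discontinuation, 19 evaluable. Two-sided alpha is 0.05.

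**Inputs not in the documents, therefore assumed.** Block size; the share of Vitamin E users; and R², the share of variance in liver-fat change explained by the strata.

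**1. The plan's own figure.** 24 × 0.80 = 19.2, so 19, split 9 and 10. SE = 3.1 × √(1/9 + 1/10) = 1.424. Noncentrality = 4.2 / 1.424 = 2.95 on 17 df. The noncentral t gives power of 79.4%, matching the stated 80%. The expected 95% half-width is about 3.01, so the width is about 6.0 points.

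**2. Does the covariate rule ever admit the strata?** Simulated with 50% women, 15–30% Vitamin E users and blocks of 2, 4 or 6: gender differed at p<0.05 in 0% of trials, and Vitamin E in 0 to 0.35%. In practice the trigger is switched off for both.

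**3. Effect of adjusting, by formula.** With both factors fitted and the arms exactly balanced on them, the residual SD is 3.1 × √(1 − R²) on 17 − 2 = 15 df.

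| R² | Power | 95% half-width |
|---|---|---|
| 0 | 78.7% | 3.04 |
| 0.05 | 80.7% | 2.96 |
| 0.10 | 82.8% | 2.88 |
| 0.20 | 86.9% | 2.72 |
| 0.30 | 90.9% | 2.54 |

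Break-even against 79.4% is at R² of about 0.017. This is optimistic, because dropout and part-filled blocks leave some imbalance.

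**4. Effect of adjusting, by simulation of the model recommended below.** Blocks of 4, 20% Vitamin E use, 19 analysed, only gender prognostic. Gender is always fitted; Vitamin E is fitted unless fewer than two users are analysed in either arm.

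| R² (gender) | t-test power | Adjusted power | Change (points) | Mean adjusted 95% CI width (t-test about 6.0) |
|---|---|---|---|---|
| 0 | 79.4% | 77.6% | -1.8 | 6.1 |
| 0.05 | 78.1% | 78.4% | +0.3 | 5.9 |
| 0.10 | 78.6% | 81.0% | +2.4 | 5.8 |
| 0.20 | 79.2% | 85.4% | +6.2 | 5.5 |
| 0.30 | 80.4% | 89.5% | +9.1 | 5.1 |

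Over the same range the t-test's type I error falls from 4.9% to 2.8%.

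**5. Without the sparse-user rule.** With both factors always fitted and neither prognostic, power falls from 78.9% to 75.9% at 20% Vitamin E use, and from 78.6% to 75.8% at 15% use. At 15% use with gender R² of 0.05, adjustment still loses: 78.8% against 77.2%. At a total R² of 0.10 split equally it is about neutral (79.3% against 80.1%).

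**The case against.** The strongest objection is that no loss has been shown. No figure in the documents says that gender or Vitamin E predicts change in liver fat, and if neither does, adjustment costs power. For Vitamin E there is some reason to expect little. Exclusion criterion 14 admits only users stable for at least six months, and a stable exposure need not predict change over the next 24 weeks. The Alternative Treatments section does credit Vitamin E with improving histology in NASH, but that is not evidence about change in liver fat among established users. This objection stands: the benefit is conditional, and at an R² near 5% there is nothing in it either way.

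A second objection is that the sparse-user rule often removes Vitamin E. At 20% use it does so in about 57% of simulated trials (about 92% at 10% use and 24% at 30%). That is correct, and it is why the rule limits the cost. The results in step 4 already include it.

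A reader might also infer that the primary test is invalid, that the 80% power is overstated, or that stratification is wasted. The documents support none of these. The t-test's departure from 5% is towards conservatism. The power was computed for the unadjusted test and reproduces. Stratification still protects the arm comparison from chance imbalance; only its benefit to the standard error is forgone.

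**Conclusion.** The point holds as one of efficiency and prespecification. The randomisation factors are absent from every stated analysis, and the covariate rule will almost never bring them in. Those two statements rest on the text and are firm.

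The size is conditional on an unknown R². For the recommended model the change in power runs from about 2 points lost if gender explains nothing, through break-even near 5%, to about 6 points gained at 20% and 9 at 30%. These figures assume 20% Vitamin E use, blocks of 4, random loss to 19, and gender as the only prognostic factor. It would go too far to say that the interval is too wide or that power is lost as a matter of fact. A possible small loss is set against a possible larger gain, in a study that describes itself as a pilot. That supports a recommended change to the plan, not a finding that the primary analysis is unsound.

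**What to change.** In Section VII, make the primary liver-fat analysis a linear model of change on arm plus the randomisation factors:

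- Always include gender.
- Include Vitamin E use unless fewer than two users are analysed in either arm, with that rule written down before database lock.
- Report the adjusted difference in percentage points with its 95% CI.
- Add the same terms to the secondary-endpoint models and the mixed models.
- Keep the two-sample t-test as a sensitivity analysis.

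If the sponsor prefers to leave a factor out, the plan should say so and give the reason.

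The cost is wording and one or two degrees of freedom. That is about 2 points of power if gender explains nothing and the sparse-user rule is used, or about 3 points if Vitamin E is always fitted and neither factor is prognostic. No data collection or trial conduct changes.

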Subjects who learn of the study through their physician or through advertisement and are interested will be asked to initiate contact with the study staff. Patients who respond to website advertising may elect to fill out a survey regarding eligibility that will ask them to provide contact information if they are willing to be contacted. Alternatively, if a patient's physician obtains the patient's permission for study staff contact, we may contact potential participants who have been identified as suitable by local providers. For patients seen clinically by the PI or other physician investigators involved in the study, the following procedures will be followed to ensure that subjects do not feel obligated to participate because of the involvement of their regular physician: The provider may mention the study to the patient and provide a flyer or consent form for the subject to take home. If this occurs, the provider will not talk further about the study unless the patient initiates the conversation by expressing interest. Alternatively, the patient's provider may mention the study and either ask the patient's permission for a different study provider to contact him/her, or provide contact information of a different study provider whom the patient can contact if interested.

Preliminary eligibility will be determined based on study staff interviews of interested subjects over the phone. Eligible subjects will then be scheduled for a screening visit.

Informed Consent

Written informed consent will be obtained by a licensed physician investigator prior to screening evaluation and testing. Subjects will be informed that they may withdraw from participation in the study at any point.

V. Study Procedures

The study will be conducted over 2 years, with subject recruitment complete after 18 months. Each eligible subject will participate in the study for 24 weeks. Following the screening visit, eligible subjects will return to the Massachusetts General Hospital Clinical Research Center (CRC) for as shown in the schema. Subjects in the Norditropin group will have 7 additional visits, and subjects in the No Treatment group will have 3 additional visits. Subjects who discontinue treatment for any reason will be asked to continue to return for study visits per their original randomization assignment.

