Patients will arrive after an 8-hour fast. For females, urine pregnancy test will be performed prior to the start of any procedures. When possible, women with regular menses will be studied within 10 days of the onset of the menstrual cycle.

1. Within one week prior to the baseline visit, subjects will come in the fasting state for a clonidine/arginine stimulation test to assess GH secretion (see methods).
2. Interval history and physical exam
3. Indirect calorimetry in the fasting state for the first 10 randomized subjects only
4. Fasting blood sample for glucose, insulin, IGF-1, AST, ALT, GGT, lipid panel, CRP, adiponectin, CK18
5. Standard 75g oral glucose tolerance test
6. DXA for quantification of total and regional fat and lean mass, VAT and SAT
7. Anthropometrics including height, weight, waist and hip circumferences, neck, mid-arm, and mid-thigh circumferences
8. Analysis of 24-hour food recall for macro- and micronutrient composition
9. Assessment of physical activity and lifestyle habits (including alcohol consumption) using questions from the 2013 Standard High School Youth Risk Behavior Survey (YRBS)
10. Instruction on reconstituting and administering Norditropin for subjects randomized to rhGH, with first injection prior to discharge

Safety Visits (2, 4, 6, and 18 weeks, Norditropin subjects only): **(1)** Interval H&P and safety assessment; **(2)** IGF-1, fasting glucose **(3)** Collection of used study drug and dispensation of new supply.

12 Week Visit: **(1)** Interval H&P and safety assessment; **(2)** IGF-1, fasting glucose **(3)** Collection of used study drug and dispensation of new supply for Norditropin subjects; **(4)** AST and ALT.

24 Week Visit: Subjects receiving treatment will be instructed to take their final Norditropin injection the night before the visit. Girls with regular menses will be studied within 10 days of the onset of the menstrual cycle. This visit will be identical to baseline with the addition of ¹H-MRS/MRI in the fasting state prior to OGTT. (clonidine/arginine stimulation test will *not* be repeated.) Indirect calorimetry will be performed only for the first 10 randomized subjects.

VI. Methods

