
75 g Oral Glucose Tolerance Test will be performed after a 12-hour fast with sampling for insulin and glucose at 0 and 120 min.

Whole Body DXA will be done to determine whole body and regional fat including DXA assessed VAT and SAT (75, 76).

Clonidine/Arginine stimulation test will be performed after 12h fast according to standardized protocol. At time 0, subjects will take clonidine 150mcg/m² (max 250mcg) PO x 1 and will receive intravenous administration of arginine hydrochloride (0.5g/kg with max dose of 30g; 30g/300 cc infusion) over 30 minutes. GH sampling will be done at baseline and 30, 60, 90 and 120 minutes.

Nutrition and Activity: 24-hour food recall will be performed and analyzed by registered dietitians at the Clinical Research Center to assess micronutrient and macronutrient intake. Questions from the CDC 2013 Standard High School Youth Risk Behavior Survey (ftp://ftp.cdc.gov/pub/data/yrbs/2013/2013_hs_questionnaire.pdf) will be used to assess physical activity (Q80-84), eating habits (Q71-79), drinking habits (Q41-45), and recent dieting (Q66-70).

Labs will be run using standard validated assays.

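### The follow-on adjusted analyses, including for liver fat, mix baseline covariates with on-study diet and activity changes; if assignment affects those changes or their reporting, the adjusted estimate is not an intention-to-treat effect.

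*Combined protocol and SAP*

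**What the plan says.** Under VII. Biostatistical Analysis, the plan first describes the test for endpoints that have just two assessments: "including the primary endpoint of liver fat, will be initially assessed using a two-sample t-test comparing mean changes between treatment groups". A second step follows: "Subsequently, adjusted analyses will be performed including as covariates any baseline characteristics that differ between treatment groups". The same sentence then names a further set of covariates: "any differential changes in nutritional intake or physical activity between treatment groups over the study duration". Because this follows directly on the liver-fat sentence, the primary endpoint is covered.

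The same section puts the analysis under the intention-to-treat principle and later adds: "The primary analysis will be an intention to treat analysis using all available data". It does not say what effect the adjusted estimate targets, how a differential change is to be judged, or that the adjusted result is exploratory.

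Four other places bear on the point:
- V. Study Procedures: "Subjects in the Norditropin group will have 7 additional visits, and subjects in the No Treatment group will have 3 additional visits".
- Randomization and Study Drug: "The study will not be blinded and placebo will not be used".
- VI. Methods, Nutrition and Activity: diet comes from a 24-hour recall, and activity and eating habits from survey questions. Both are self-reported. They are collected at baseline and again at week 24, of which the plan says "This visit will be identical to baseline with the addition of" the MRS/MRI scan.
- VI. Methods, Lifestyle Counseling: subjects are counselled at baseline, week 12 and week 24, with no distinction by arm.

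**The concern.** Assignment cannot change a baseline characteristic, so adjusting for one leaves the ITT effect as the target. A change in diet or activity during the study is different. If being assigned to rhGH, or to no treatment, leads subjects to eat or exercise differently, that difference is part of the effect of assignment, and a model that holds it fixed removes that part. If knowing the assignment only alters what subjects report, the model adjusts for something that did not happen.

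Nor does the adjusted model reliably isolate a direct drug effect. The measures are self-reports with error, and diet or activity may share unmeasured causes with liver fat.

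The plan lists both kinds of covariate together. Whenever the lifestyle rule is triggered, the adjusted model as described therefore no longer provides a purely baseline-adjusted ITT estimate. A reader could take the reported figure for the treatment effect corrected for lifestyle. The Sample Size section treats 4.2 points as the smallest clinically relevant difference, so a shift of about a point could move an estimate across that line.

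**Working it through.** **1. The plan's own figure.** Inputs from Sample Size and Power Calculations: SD 3.1, effect 4.2, 19 evaluable subjects. Alpha is 0.05 two-sided (section VII) and allocation is 1:1 (section V), so take 10 v 9.

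Noncentrality = 4.2 / (3.1 × √(1/10 + 1/9)) = 4.2 / 1.424 = 2.95. With 17 degrees of freedom (critical t 2.11) the power is 79.4%, against 80% stated. The detectable effect at 80% power is 4.23 points. The stated power is therefore that of the unadjusted t-test.

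**2. Size of the departure.** Write effects as reductions in liver fat. Let *b* be the points of reduction per SD of lifestyle improvement, and *g* the lifestyle gap in SD caused by assignment (positive if the rhGH arm improves more). Then

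expected adjusted estimate = ITT effect − *b* × *g*.

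The documents give neither *b* nor *g*. Assume *b* = 1.05 and a true ITT effect of 4.2. The simulation used 10 v 9 subjects, a within-arm SD of 3.1 and 200,000 replicates. Entry means p < 0.05 for the lifestyle difference, which is an assumed reading of differential.

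| Gap *g* | Arithmetic | Simulated mean | Chance of entry |
|---|---|---|---|
| +1 | 4.2 − 1.05 = 3.15 | 3.15 | 54% |
| +0.5 | 4.2 − 0.525 = 3.675 | 3.67 | 18% |
| +0.25 | 4.2 − 0.2625 = 3.94 | 3.94 | 8% |
| 0 | 4.20 | 4.20 | 5% |
| −0.5 | 4.2 + 0.525 = 4.725 | 4.73 | 18% |
| −1 | 4.2 + 1.05 = 5.25 | 5.26 | 54% |

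The unadjusted estimate averages 4.19 to 4.21 in every row, with about 79% power. The departure scales with *b*: at 1.5 points per SD and a 1 SD gap it is 1.5 points. If the true ITT effect is zero, with *b* = 1.05 and a 1 SD gap, the adjusted test rejects in about 10% of trials and the t-test in about 5%.

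**3. Self-report.** With reliability *r*, the departure becomes *r* × *b* × *g*. At *r* = 0.5 and a true 1 SD gap: 4.2 − 0.5 × 1.05 = 3.68. That is neither the ITT effect (4.2) nor the direct effect (3.15). If only reporting differs by 1 SD, the adjusted estimate averages about 3.15 or 5.25, although the ITT and direct effects are both 4.2.

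**4. Shared causes, no drug effect.** Suppose an unmeasured cause correlates 0.6 with lifestyle change and −0.6 with liver-fat change. The adjusted estimate is then off by 0.6 × 0.6 × 3.1 = 1.12 points at a 1 SD gap, and the adjusted test rejects in 10.6% of trials. At a 0.5 SD gap it is off by 0.56 points (6.7%). Correlations of 0.3 and −0.3 at 1 SD give 0.3 × 0.3 × 3.1 = 0.28 points (5.2%). The t-test stays at 5%.

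**5. What the lifestyle model offers when assignment has no effect on lifestyle.** With *g* = 0 and *b* = 1.05, in the 5% of trials where the covariate enters by chance, the unadjusted estimate averages 5.2 or 3.1, depending on which arm happened to improve. The adjusted one stays near 4.2, so it corrects a chance error of about 1 point. Several measures raise the entry rate: 1 − 0.95⁵ = 23% for five independent measures and 1 − 0.95¹⁰ = 40% for ten. Adjusting in every trial would raise power from 79% to about 81% at 1.05 points per SD, or 86% at 1.5.

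**The case against.** The strongest reply has three parts.

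**The main analysis is already protected.** The t-test comes first, the adjusted analyses follow, the primary analysis is called intention-to-treat, and the power matches the t-test. This stands. A reader might infer that the primary liver-fat result is biased or that the adjusted estimate replaces it. The text supports neither, although it only implies that the t-test is the main analysis.

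**Nothing shows that assignment changes lifestyle.** Counselling times are the same in both arms, and the treated arm's extra visits (weeks 2, 4, 6 and 18) list history and examination, safety, laboratory tests and drug supply. This also stands. A reader might infer from the open-label design and the 7 v 3 visits that a lifestyle gap will arise. Those features make it possible and no more. Without an effect on lifestyle or its reporting, the adjustment causes no bias.

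**The lifestyle model is a legitimate robustness check.** In trials where the rule fires it removes chance imbalance. Even with a real gap it can be closer to the truth. Given entry in the direction of the gap, and against a truth of 4.2, the unadjusted and adjusted means are 5.06 and 3.95 at 0.25 SD, 4.86 and 3.67 at 0.5 SD, and 4.54 and 3.15 at 1 SD. The adjusted mean is worse only at 1 SD. This is a good reason to keep the model, but not to place it in the same adjusted efficacy analysis as the baseline covariates with no label. The plan speaks of adjusted analyses in the plural, so separate models are conceivable, but it does not specify them.

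**Conclusion.** The point holds as a limited one, worth acting on because the remedy is cheap. The follow-on adjusted estimate, including for liver fat, is not an ITT effect if assignment affects lifestyle or its reporting, and the departure can go either way. When the rule is triggered, the plan as written also provides no purely baseline-adjusted estimate. At the assumed 1.05 points per SD the departure is about 0.5 points at a 0.5 SD gap and about 1 point at 1 SD; it is zero with no gap.

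All these sizes rest on assumed path strengths, gaps, reliabilities and correlations that the documents do not give, and the entry rates on a p < 0.05 trigger applied to a single covariate. The t-test, its type I error and the stated power are untouched. It would also go too far to conclude that the lifestyle-adjusted model has no value and should be abandoned; step 5 of the working shows what it can contribute.

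**What to change.** In VII. Biostatistical Analysis:
- Restrict the covariates of the adjusted efficacy analyses to baseline variables.
- State that the unadjusted or baseline-adjusted comparison answers Aim 1.
- Report changes in diet and activity by arm descriptively.
- Keep any lifestyle-adjusted model as a separate exploratory sensitivity analysis, labelled as not an ITT effect and as dependent on no unmeasured confounding. State which measures enter it and how a differential change is judged.

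The cost is SAP wording; no data are lost. If lifestyle is prognostic and unaffected by assignment, the main adjusted model gives up the correction of chance imbalance and the modest precision gain quantified in step 5. Retaining the exploratory model keeps that information available to the reader.

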Sample Size and Power Calculations: The study is designed to yield pilot data, with the primary endpoint being change in hepatic fat fraction. As we do not have preliminary data on this measure in an adolescent population, we used a published standard deviation (SD) of 3.1%. A sample size of 24 subjects, with up to 20% discontinuation rate, yielding 19 evaluable patients, has 80% power to detect a 4.2 percentage point treatment effect on liver fat (e.g., a reduction from 7% liver fat to 2.8% liver fat), which is the minimum difference that would be clinically relevant, as absolute reductions of ≥ 4 -5% liver fat have been considered clinically relevant in previous publications (77, 78). For secondary variables of interest, the study is has 80% power to detect a treatment difference of approximately 1.4 SD.

VIII. Risks and Discomforts

Radiation: Subjects will have 2 DXA scans over 6 months, for a total radiation risk from both scans of 2 microSieverts. This radiation exposure is minimal and does not pose excessive risk to subjects. Female subjects must have a negative pregnancy test before DXA scanning.

Blood Drawing: Blood sampling volumes will be as follows: screen 27cc, baseline and 24 week visit 99cc, safety visits 5-8cc each (5 cc at 2 and 4 weeks, 8cc at 6, 12, 18 weeks). The total blood drawing will be 286cc over 6 months. The maximum blood drawn during any 8 week period (screen+baseline+2wk+4wk) will be no more than 140cc. Body weight ≥ 50 kg and Hgb ≥ 11 g/dL will be required to participate, which will ensure that the blood volume sampled is within guidelines and does not pose significant risk to subjects.

Blood drawing may cause discomfort, pain, and bruising.

MRI/MR spectroscopy: MRI and MR spectroscopy will be performed using FDA approved devices and pulse sequences, and there are no known foreseeable risks associated with exposure to MRI. Subjects will be carefully screened for the presence of metallic implants (e.g., vascular clamps) prior to MR scanning. Some

subjects report claustrophobia during MRI scans, and if any patient experiences discomfort during the scan, the procedure will be aborted and not repeated without the subject's consent.

Oral Glucose Tolerance Test: Oral glucose tolerance test has no significant risks. Some subjects may experience nausea or lightheadedness during the procedure, and supportive nursing care will be provided.

Clonidine/Arginine Stimulation:

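### The 80% power claimed at about 1.4 SD for secondary variables does not hold for respiratory quotient, which is measured in only 10 of the 24 subjects

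*Combined protocol and SAP*

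**What the plan says.** All references are to the combined protocol and SAP.

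- Section VII (Biostatistical Analysis), Sample Size and Power Calculations, opens with "The study is designed to yield pilot data". It bases the primary calculation on 24 subjects "with up to 20% discontinuation rate, yielding 19 evaluable patients".
- The same paragraph ends with a single power statement for the other endpoints: "For secondary variables of interest, the study is has 80% power to detect a treatment difference of approximately 1.4 SD". It names no exception and does not say which variables it covers.
- The opening paragraph of section VII lists the secondary endpoints. The list ends with "fasting and 2-hour glucose and insulin, HbA1c, and respiratory quotient measured by indirect calorimetry". Nothing there marks respiratory quotient as exploratory or descriptive.
- Section V (Study Procedures), Baseline Visit, item 3 reads: "Indirect calorimetry in the fasting state for the first 10 randomized subjects only". The 24 Week Visit repeats the limit: "Indirect calorimetry will be performed only for the first 10 randomized subjects".
- Section VII says that changes in variables measured only at baseline and 6 months "will be initially assessed using a two-sample t-test comparing mean changes between treatment groups", two-tailed at 0.05. Respiratory quotient is such a variable.

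**The concern.** The power sentence comes straight after a calculation on 19 evaluable subjects and is worded as if it covered the secondary endpoints generally. Change in respiratory quotient can exist for at most 10 of 24 subjects (42%), about half of the 19 behind the figure.

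A reader who applies the stated power to respiratory quotient would expect a true 1.4 SD effect to be missed about one time in five. With 10 subjects it would be missed about one time in two. A non-significant result on this endpoint would then be taken as firmer evidence of no effect than the data could support. No sample size, stopping rule or primary analysis depends on this endpoint.

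**Working it through.** **Inputs from the documents.** Two-sample t-test on change, two-sided alpha 0.05, 1:1 allocation, 24 randomised and 19 evaluable (section VII; allocation from section V). Primary SD 3.1 and effect 4.2 percentage points (section VII). Calorimetry in the first 10 randomised subjects (section V).

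**Formulas.** With arm sizes n1 and n2 and a true difference of d SD:

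- degrees of freedom: df = n1 + n2 − 2
- noncentrality: λ = d / √(1/n1 + 1/n2)
- power = P(|T| > t(0.975, df)), where T is noncentral t with df and λ
- 95% CI half-width in SD units = t(0.975, df) × √(1/n1 + 1/n2)

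**Step 1: reproduce the plan's figure.** 24 × 0.8 = 19.2, so 19 evaluable, split 10 v 9. √(1/10 + 1/9) = 0.459; df = 17; critical t = 2.110; λ = 1.4 / 0.459 = 3.05. Power is 81.9%, and 80% power needs 1.37 SD. The primary effect is 4.2 / 3.1 = 1.355 SD, with power 79.4%. Both are within 2 points of 80%, so the stated 1.4 SD is a 19-subject, two-sided t-test figure.

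**Step 2: respiratory quotient, best case.** 10 subjects, 5 v 5, no losses. √(1/5 + 1/5) = 0.632; df = 8; critical t = 2.306; λ = 1.4 / 0.632 = 2.21. Power is 49.5%, and 80% power needs 2.02 SD. A simulation of 200,000 trials gave 49.6%.

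**Step 3: with the plan's loss rate.** Assume the 20% applies within the subset: 10 × 0.8 = 8, split 4 v 4. √(1/4 + 1/4) = 0.707; df = 6; critical t = 2.447; λ = 1.4 / 0.707 = 1.98. Power is 38.5%, and 80% power needs 2.38 SD.

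| Evaluable split | Power at 1.4 SD | Difference for 80% power | 95% CI half-width |
|---|---|---|---|
| 10 v 9 (all subjects) | 81.9% | 1.37 SD | 0.97 SD |
| 5 v 5 (calorimetry, best case) | 49.5% | 2.02 SD | 1.46 SD |
| 6 v 4 | 47.9% | 2.07 SD | 1.49 SD |
| 7 v 3 | 43.1% | 2.21 SD | 1.59 SD |
| 4 v 4 (20% loss assumed) | 38.5% | 2.38 SD | 1.73 SD |

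The uneven rows are shown because the plan says "Permuted block randomization will be performed, stratified by gender and use of Vitamin E" and gives no block size, so the first 10 subjects need not divide equally. An uneven split only lowers the power.

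**Step 4: would a more lenient method rescue the figure?** At 5 v 5 the normal approximation gives 60.0% (1.77 SD for 80%), and a one-sided t-test gives 64.7% (1.73 SD). Neither is the planned test and neither reaches 80%. With equal arms, power at 1.4 SD is 79.6% with 9 per arm and 84.1% with 10 per arm, so about twice the subset would be needed.

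**The case against.** The strongest reply concerns scope. The sentence does not say that it covers every secondary endpoint. It refers to an undefined group of secondary variables, directly after the 19-subject calculation, and respiratory quotient does not appear in the Specific Aims. It could be read as covering only endpoints carried by the full sample. That reading is possible, but nothing in the text exempts a listed secondary endpoint. If respiratory quotient is outside the sentence, the plan gives no power or precision for it at all. The same rewording settles both readings.

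Second, the limit to 10 subjects is stated openly at both visits, and the study is described as a pilot. Both are true, and they keep the point minor. Neither makes the numerical claim right for this endpoint.

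Third, the lower power figures depend on assumptions. The plan says up to 20% discontinuation, and section V asks subjects who stop treatment to keep attending, so 8 evaluable is towards the pessimistic end. This stands. The part that needs no loss assumption is 10 subjects, with about 50% power at best.

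A reader might also infer that change in HbA1c, in the same list of secondary endpoints, cannot be measured, because the written visit lists name the assay only at screening. The documents do not support that. Section V refers to a visit schema that is not reproduced in the available text, so a 24-week HbA1c may well be planned.

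**Conclusion.** The sentence is wrong as written for respiratory quotient. Power at 1.4 SD is about 50% at best, against the stated 80%, and 80% power needs about 2.0 SD. With 8 evaluable subjects the figures are about 39% and 2.4 SD. The calculation assumes normally distributed changes with equal variance; the 5 v 5 split and the 20% loss within the subset are assumptions that the documents do not give. The conclusion depends on neither, because 5 v 5 without losses is the most favourable case.

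Two broader inferences should be resisted. One is that the secondary power statement is wrong in general: it reproduces for endpoints measured in all subjects at baseline and 24 weeks and compared by the t-test. The other is that it is thereby confirmed for every remaining secondary endpoint. Section VII assigns variables with three or more time points, with IGF-1, AST and ALT as its examples, to mixed models testing a time-by-treatment interaction. The t-test calculation does not establish power for those, in either direction.

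Severity is minor. The primary endpoint and its power are unaffected.

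**What to change.** In section VII, Sample Size and Power Calculations:

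1. Limit the 1.4 SD statement to secondary endpoints measured in all subjects at baseline and 24 weeks and analysed by the two-sample t-test.
2. Add that respiratory quotient has a planned n of 10, with 80% power only for a difference of about 2.0 SD if all 10 are evaluable and split equally, or about 2.4 SD if 8 are evaluable (labelled as an assumption).
3. State that respiratory quotient will be reported with a 95% confidence interval, so that its imprecision is visible whatever the p-value.

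The cost is wording only. No visit, assay, sample size or primary analysis changes. The stated power for respiratory quotient becomes less favourable.
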